1. Protocol Summary (Table 3: Schedule of Activities: Vehicle-Controlled Period; Table 4: Schedule of Activities: Long-Term Safety Period); Section 8.1.5.1, Demographics and General Medical History; Section 8.4.3, Vital Signs, Height, and Weight

Description of change: Added guidance to capture height and weight of not only each participant, but also both parents of each participant (if available), and to record these data in the EDC.

Rationale for change: To provide clarity that the growth measurements will be entered into the EDC and evaluated at the end of the study.

[REDACTED]

3. Section 2, Introduction

Description of change: Revised the order of the sections for clarity and added text.

- Moved Section 2.2, Study Rationale, to Section 2.3.
- Moved Section 2.2.1, Scientific Rationale for Study Design, to Section 2.3.1.
- Moved Section 2.2.2, Justification for the Selected Treatment Regimen, to Section 2.3.2.
- Moved Section 2.2.2.2, INCB 18424-303 and INCB 18424-304, to Section 2.2.1 and changed the heading to INCB 18424-303 and INCB 18424-304: Phase 3 Adolescent/Adult Studies.
- Moved Section 2.2.2.3, INCB 18424-102: Pharmacokinetic Pediatric Study, to Section 2.2.2.
- Created Section 2.2, Pivotal Phase 3 Studies and Pilot Pediatric Study, for Section 2.2.1, INCB 18424-303 and INCB 18424-304: Phase 3 Adolescent/Adult Studies, and Section 2.2.2, INCB 18424-102: Pharmacokinetic Pediatric Study.

- Moved Section 2.2.2.1, INCB 18424-206, to part of Section 2.3.2, Justification for the Selected Treatment Regimen, and added text to provide further information for the justification of the selected treatment regimen.

Rationale for change: Administrative corrections.

4. Section 5.2, Exclusion Criteria (Criteria 2h, 3b, and 3d)

Description of change:

- Exclusion Criterion 2h: Added a criterion to exclude participants who are on maintenance dialysis.
- Exclusion Criterion 3b: Added text to clarify that the laboratory test criterion for the ULN does not include for serum creatinine levels.
- Exclusion Criterion 3d: Added a clinical laboratory test criterion for the lower limit of the estimated GFR.

Rationale for change: To address Canadian Health Authority request.

5. Section 5.2, Exclusion Criteria (Criteria 6c)

Description of change: Clarified the requirement for inactivated vaccines.

Rationale for change: To simplify the immunization requirement.

6. Section 6.1, Study Treatments Administered; Section 6.1.1, Study Treatment Application Guidance

BSA	body surface area
CI	confidence interval
CRF	case report form
CTCAE	Common Terminology Criteria for Adverse Events
EASI	Eczema Area and Severity Index
EASI75	≥ 75% improvement in EASI score
eCRF	electronic case report form
EOT	end of treatment
ET	early termination
FDA	Food and Drug Administration
IGA	Investigator's Global Assessment
IGA-TS	Investigator's Global Assessment Treatment Success (IGA score of 0 or 1 with ≥ 2-grade improvement from baseline)
ITT	intent-to-treat
LTS	long-term safety
MedDRA	Medical Dictionary for Regulatory Activities
MI	multiple imputation
MMRM	mixed-model repeated measures
NRI	nonresponder imputation
NRS	numerical rating scale

Abbreviation	Term
ANC	absolute neutrophil count
PP	per protocol
PT	preferred term
SAP	Statistical Analysis Plan
SOC	system organ class
TCI	topical calcineurin inhibitor
TCS	topical corticosteroid
TEAE	treatment-emergent adverse event
WHO	World Health Organization
VC	vehicle-controlled

1. INTRODUCTION

Study INCB 18424-305 is a randomized, double-blind, vehicle-controlled study with an LTS period in pediatric participants aged ≥ 2 to < 12 years with AD eligible for topical therapy. This Phase 3 study will be conducted at roughly 60 sites in the United States and Canada. Approximately 315 participants will be randomized 2:2:1 to blinded treatment with either ruxolitinib 1.5% cream BID, ruxolitinib 0.75% cream BID, or vehicle cream BID; stratification will be by baseline IGA score and age. Enrollment will be capped such that no more than approximately 25% of randomized participants have a baseline IGA score of 2. At least 40% of the overall study population will consist of children aged ≥ 2 to 6 years. In this trial, participants will apply blinded study treatment for 8 weeks followed by a randomized 44-week LTS extension period. In the LTS period, participants initially randomized to vehicle cream will apply either ruxolitinib 0.75% or 1.5% cream BID; this will replicate the design of the earlier pivotal studies (INCB 18424-303 and INCB 18424-304) in adolescents and adults with AD.

The purpose of this SAP is to provide details of the statistical analyses that have been outlined in the INCB 18424-305 Protocol. The Department of Biostatistics or designee will execute the scope of this plan [REDACTED]
[REDACTED].

2. STUDY INFORMATION, OBJECTIVES, AND ENDPOINTS

2.1. Protocol and Case Report Form Version

This SAP is based on INCB 18424-305 Protocol [Amendment 6](#) dated 22 FEB 2023 and CRFs approved 10 JAN 2023. Unless superseded by an amendment, this SAP will be effective for all subsequent Protocol amendments and eCRF versions.

2.2. Objectives and Endpoints

[Table 1](#) presents the objectives and endpoints.

Table 1: Objectives and Endpoints

Objectives	Endpoints
Primary	
To establish the efficacy of ruxolitinib cream in participants with AD.	Proportion of participants who achieve IGA-TS at Week 8.
Key Secondary	
To further assess the treatment effects of ruxolitinib cream.	
• Proportion of participants with a \geq 4-point improvement in Itch NRS score from baseline to Week 8.• Proportion of participants with a \geq 4-point improvement in Itch NRS score from baseline to Day 7 (Week 1).• Proportion of participants with a \geq 4-point improvement in Itch NRS score from baseline to Day 3.
Secondary	
To evaluate the safety and tolerability of ruxolitinib cream.	The type, frequency, and severity of AEs and changes from baseline in physical examinations, vital signs, height, weight, and laboratory data for hematology and serum chemistry.
To further evaluate the efficacy of ruxolitinib cream.	
• Proportion of participants who achieve IGA-TS at Weeks 2 and 4.• Proportion of participants with a \geq 4-point improvement in Itch NRS score from baseline to Weeks 2 and 4.• Proportion of participants who achieve EASI75 at Weeks 2, 4, and 8.• Time to achieve Itch NRS score improvement of at least 2 or 4 points.

Table 1: Objectives and Endpoints (Continued)

Objectives	Endpoints
[REDACTED]	

Table 1: Objectives and Endpoints (Continued)

Objectives	Endpoints

3. STUDY DESIGN

[figure not shown]
This is a randomized, double-blind, VC study with an LTS period in pediatric participants aged ≥ 2 to < 12 years with AD eligible for topical therapy. For participants who meet all study inclusion criteria and none of the exclusion criteria, study drug will be assigned at the Day 1/baseline visit. Participants will be randomized 2:2:1 to blinded treatment with either ruxolitinib 0.75% cream BID, ruxolitinib 1.5% cream BID, or vehicle cream BID, with stratification by baseline IGA score and age. Enrollment will be capped, such that no more than approximately 25% of randomized participants have a baseline IGA score of 2. At least 40% of the overall study population will consist of children aged ≥ 2 to 6 years.

Participants who complete Week 8 assessments with no additional safety concerns will continue into the 44-week LTS period with the same treatment regimen, except those initially randomized to vehicle cream who will be rerandomized (1:1) in a blinded manner to 1 of the 2 active treatment groups (ruxolitinib 0.75% or 1.5% cream BID). The IGA score required for participants to enter the LTS period is 0 to 4, and participants must have a %BSA in the range of 0% to 20% (excluding the scalp).

Following the end of treatment (Week 52/EOT or ET), all participants will have a safety follow-up visit 30 days later (or 30 days after the last application of study treatment if the Week 52/EOT or ET visit was not performed); this visit will evaluate the safety and duration of response (refer to Protocol [Amendment 6](#)).

Figure 1 presents the study design schema.

Figure 1: Study Design Schema

- At Week 8 (LTS baseline), participants initially on vehicle during the VC period will be rerandomized to either ruxolitinib 1.5% or 0.75% cream BID. Participants initially randomized to either ruxolitinib 0.75% or 1.5% BID will continue their treatment through the LTS period.

** Treatment is ceased 3 days after clearing of AD lesions. Treatment is restarted if AD lesions recur. There is no limit on the number of treatment cycles during the 44-week LTS.

3.1. Randomization

In the VC period, the IRT system will assign approximately 315 participants in a 2:2:1 ratio to ruxolitinib 1.5% cream BID, ruxolitinib 0.75% cream BID, or vehicle cream BID, respectively. Additionally, participants will be stratified by baseline IGA score (2 or 3) and age (2-6 years or 7 to < 12 years).

Participants who complete Week 8 assessments with no safety concerns will continue into the 44-week LTS period with the same treatment regimen, except that those initially randomized to vehicle cream who will be rerandomized (1:1) in a blinded manner to 1 of the 2 active treatment groups (ruxolitinib 0.75% or 1.5% cream BID).

3.2. Control of Type I Error

For the primary and key secondary analyses, an overall 2-sided Type I error of 0.05 will be used.

A graphical procedure with gatekeeping testing strategy for the primary and key secondary analyses will be implemented. The underlying procedure is derived using the methodology developed by Bretz et al (2009). The method will guarantee a strong control of the family-wise error rate.

In Step 1, 2 families of 4 elementary hypotheses tests at Week 8 are grouped according to treatment comparison between each ruxolitinib cream group and the vehicle cream group, where

- Family 1 (1.5% BID vs vehicle):
 - H11: proportion of participants who achieve IGA-TS
 - H12: proportion of participants with a \geq 4-grade improvement in Itch NRS score over baseline
- Family 2 (0.75% BID vs vehicle):
 - H21: proportion of participants who achieve IGA-TS
 - H22: proportion of participants with a \geq 4-grade improvement in Itch NRS score over baseline

[figure not shown]
Step 2 has 2 families of 4 hypotheses tests:

- Family 3 (1.5% BID vs vehicle and 0.75% BID vs vehicle on Day 7 Itch NRS):
 - H13: proportion of participants with a \geq 4-grade improvement in Itch NRS score over baseline to Day 7 (Week 1) between 1.5% BID and vehicle
 - H23: proportion of participants with a \geq 4-grade improvement in Itch NRS score over baseline to Day 7 (Week 1) between 0.75% BID and vehicle
- Family 4 (1.5% BID vs vehicle and 0.75% BID vs vehicle on Day 3 Itch NRS):
 - H14: proportion of participants with a \geq 4-grade improvement in Itch NRS score over baseline to Day 3 between 1.5% BID and vehicle
 - H24: proportion of participants with a \geq 4-grade improvement in Itch NRS score over baseline to Day 3 between 0.75% BID and vehicle

[figure not shown]
To control the overall Type I error rate, 2-sided $\alpha = 0.05$, the Bonferroni's method will be used. In Step 1, within Family 1 and 2, the endpoints are tested in a fixed sequence at a Bonferronized 2-sided $\alpha = 0.025$ level. The key secondary endpoint will be tested only if the associated primary endpoint is rejected. For any treatment strength, if the 2 related null hypotheses can be rejected, then the fixed sequence for the other treatment strength can be conducted at the 2-sided $\alpha = 0.05$ level. If all null hypotheses in Family 1 and 2 are rejected, in Step 2, the endpoints in Family 3 (H13 and H23) will be tested using Bonferroni-Hochberg's procedure with overall 2-sided $\alpha = 0.05$ level. If both hypotheses in Family 3 are rejected, the endpoints in Family 4 (H14 and H24) will be tested similarly using Bonferroni-Hochberg's procedure with overall 2-sided $\alpha = 0.05$ level. The approach is visualized in [Figure 2](#).

Figure 2: Control of Overall Type I Error Rate

Step 1:

Step 2:

3.3. Sample Size Considerations

Approximately 315 participants will be randomized 2:2:1 to blinded treatment with either ruxolitinib 1.5% cream BID, ruxolitinib 0.75% cream BID, or vehicle cream BID. The sample size calculation is based on the Fisher exact test for the primary efficacy endpoint. Based on the results from the 2 pivotal studies in adolescents and adults with AD (INCB 18424-303 and INCB 18424-304), the response rate of IGA-TS at Week 8 is assumed to be 51% and 47% for the active arms (ie, 1.5% BID and 0.75% BID, respectively) versus 14% for placebo.

Using a 2-sided alpha of 0.025, the sample size will have > 95% power to detect a difference between each of the 2 active treatment groups versus the vehicle. In addition to providing adequate power for efficacy variables, the sample size is determined to provide a large database for safety evaluations.

3.4. Schedule of Assessments

Refer to Protocol [Amendment 6](#) dated 22 FEB 2023 for a full description of all study procedures and assessment schedules for this study.

4. DATA HANDLING DEFINITIONS AND CONVENTIONS

4.1. Scheduled Study Evaluations and Study Periods

4.1.1. Day 1

Day 1 is the date that the first application of ruxolitinib cream or vehicle cream is administered to the participants in the specific period.

For randomized participants not treated with any study drug, Day 1 is defined as the day of randomization.

4.1.2. Study Day

If a visit/reporting date is on or after Day 1, then the study day at the visit/reporting date will be calculated as

$$\text{Day \#} = (\text{visit/reporting date} - \text{Day 1 date} + 1).$$

If the visit/reporting date is before Day 1, then the study day at the visit/reporting date will be calculated as

$$\text{Day \#} = (\text{visit/reporting date} - \text{Day 1 date}).$$

A study day of -1 indicates 1 day before Day 1.

4.1.3. Baseline Value

Baseline is the last nonmissing measurement obtained before or on the day of first application of ruxolitinib cream or vehicle cream for the VC period.

For randomized participants not treated with any study drug, baseline is defined as the last nonmissing assessment before or on the day of randomization for all parameters.

For participants who continue in the LTS period, baseline for LTS is defined as follows:

- For efficacy evaluation, baseline is the last nonmissing measurement obtained before or on the day of first application of study treatment in the VC period.
- For safety evaluation, for participants who cross over from vehicle to ruxolitinib cream, baseline is the last nonmissing measurement obtained before or on the day of first application of ruxolitinib cream in the LTS period; for participants on ruxolitinib cream in both periods, baseline is the last nonmissing measurement obtained before or on the day of first application of study treatment in the VC period.

When scheduled assessments and unscheduled assessments occur on the same day and time of the assessment or time of first application is not available, use the following convention to determine baseline:

- If both a scheduled and an unscheduled visit are available on the day of the first application and the time is missing, use the scheduled assessment as baseline.
- If all scheduled assessments are missing on the day of the first application and an unscheduled assessment is available, use the unscheduled assessment as baseline.

4.1.4. Last Available Value

The last available value is the last nonmissing measurement obtained after starting ruxolitinib cream or vehicle cream and within 30 days after the last application of ruxolitinib cream or vehicle cream, or before the first application of ruxolitinib cream in the next period, whichever is earlier.

4.1.5. Handling of Missing and Incomplete Data

In general, values for missing dates will not be handled unless methods for handling missing dates are specified in this section or relevant sections. The original reported dates collected on the eCRF should be used in all relevant listings. The following rules will be used for handling partial dates for analyses requiring dates.

For response endpoints, all nonresponders, as well as all participants who are missing postbaseline values at Week 8, will be defined as nonresponders for the NRI analysis.

For continuous endpoints, any participant who is missing postbaseline values may have missing data handled using MMRM or MI under the missing-at-random assumption. The MMRM model implicitly adjusts for missing data through a variance-covariance structure.

For other endpoints, missing observations will be handled as detailed in the specific sections addressing each analysis.

4.2. Variable Definitions

4.2.1. Body Mass Index

Body mass index will be calculated as follows:

$$\text{Body mass index (kg/m}^2\text{)} = (\text{weight [kg] / (height [m])}^2$$

4.2.2. Prior and Concomitant Therapy

Prior therapy is defined as any nonstudy therapy started before the first application of study treatment.

Concomitant therapy is defined as any nonstudy therapy that is started accordingly:

- Before the date of first application of study treatment and is ongoing throughout the study or ends on/after the date of first application of study treatment
- On/after the date of first application of study treatment and is ongoing or ends during the course of study treatment

A prior therapy could also be classified as "both prior and concomitant therapy" if the end date is on or after the first application of study treatment. In the listing, it will be indicated whether a therapy is prior only, concomitant only, or both prior and concomitant.

For the purposes of analysis, all therapies will be considered concomitant therapies unless the therapies can unequivocally be defined as not concomitant.

5. STATISTICAL METHODOLOGY

5.1. General Methodology

Unless otherwise noted, SAS® software (SAS Institute Inc, Cary, NC; v9.1 or later) will be used for the generation of all tables, graphs, and statistical analyses. Descriptive summaries for continuous variables will include, but not be limited to, the number of observations, mean, standard deviation, median, minimum, maximum, first quartile, third quartile, and 95% CI. Descriptive summaries for categorical variables will include the number and percentage of participants in each category.

5.2. Treatment Groups

This is a randomized, double-blinded, VC study followed by a LTS extension period. Data will be summarized based on treatment regimen that was assigned (ITT) or that the participant actually applied (safety).

During the VC period, the treatment groups will be 1.5% BID, 0.75% BID, and vehicle.

For the LTS period, the treatment groups will be 1.5% BID, 0.75% BID, vehicle to 1.5% BID, and vehicle to 0.75% BID.

5.3. Analysis Populations

5.3.1. Intent-to-Treat Population

All participants who are randomized to the study constitute the ITT population. Treatment groups for this population will be defined according to the treatment assignment at the time of randomization regardless of the actual study treatment the participant might apply during their participation in the study.

The ITT population will be used for the summary of demographics, baseline characteristics, participant disposition, and analyses of all efficacy data in the VC period.

5.3.2. Per Protocol Population

Participants in the ITT population who are considered to be sufficiently compliant with the Protocol compose the PP population, which is defined for supportive sensitivity analyses for the primary endpoint in the VC period. Participants with important protocol deviations, as defined in Section 6.3, will be excluded from the PP population.

5.3.3. Safety Population

All randomized participants who applied ruxolitinib cream or vehicle cream at least once will constitute the safety population. Treatment groups for this population will be determined according to the actual treatment the participant applied on Day 1 regardless of assigned study treatment.

All safety analyses will be conducted using the safety population.

[REDACTED]

5.3.5. Long-Term Safety Evaluable Population

All participants who applied study drug at least once during the LTS period will constitute the LTS evaluable population. All efficacy and safety analyses for the LTS period will be conducted with the LTS evaluable population.

[REDACTED]

[REDACTED]

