10.2. Populations for Analysis

[Table 12](#) presents the populations for analysis.

Table 12: Populations for Analysis

Population	Description
ITT	The ITT population includes all randomized participants. Treatment groups for this population will be defined according to the treatment assignment at randomization.
PP	The PP population includes randomized participants who are considered to be sufficiently compliant with the Protocol. In general, the following are important protocol deviations that may significantly affect the primary analysis: Missing data for the primary endpoint Overall application compliance less than 80% during the VC period Participants with one or more such deviations will be excluded from the PP population. In addition, important protocol deviations related to inclusion/exclusion criteria, discontinuation criteria, and use of prohibited concomitant medications will be reviewed. Decisions as to whether any of these deviations warrant exclusion from the PP population will be made prior to unblinding.
Safety	The safety evaluable population includes all participants who applied study cream at least once. Treatment groups for this population will be determined according to the actual treatment the participant received on Day 1.
LTS evaluable	All analyses for the LTS period will be conducted with the LTS evaluable population, which includes all participants who applied study cream at least once during the LTS period.
	[REDACTED]

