6.2. Disposition of Participants

The number and percentage of participants who were randomized, who were treated, who completed the VC period, who discontinued study treatment, or who withdrew from the study during the VC period with a primary reason for discontinuation will be summarized and listed for the ITT population during the VC period.

The number and percentage of participants who were treated, who completed the LTS period, who were ongoing treatment during the LTS period, who discontinued study treatment, or who withdrew from the study during the LTS period with a primary reason for discontinuation, will be summarized and listed for the LTS evaluable population in the LTS period.

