9.1. General Considerations

The analyses in this section will be provided for the safety population in the VC period and for the LTS evaluable population in the LTS period. Cumulative TEAEs across the treatment periods (VC and LTS periods) will be summarized. Summary tables may be replaced with listings when appropriate. For instance, an AE frequency table may be replaced with a listing if it only contains a few unique PTs reported on relatively few participants.

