APPENDIX A. PLANNED TABLES, FIGURES, AND LISTINGS

This appendix provides a list of the planned tables, figures, and listings for the Clinical Study Report. Shells are provided in a separate document for tables that are not in the most current Standard Safety Tables.

The list of tables, figures, and listings are to be used as guidelines. Modifications of the lists that do not otherwise affect the nature of the analysis will not warrant an amendment to the SAP.

Tables

Table No.	Title	Population	Standard
Baseline Demographic and Characteristic			
1.1.1	Analysis Populations	All	X
1.1.2.1	Summary of Participant Disposition in the VC Period	ITT	X
1.1.2.2	Summary of Participant Disposition in the LTS Period	LTS Evaluable	X
1.1.3	Summary of Number of Participants Enrolled by Country and Site	ITT	X
1.1.4.1	Summary of Protocol Deviations During the VC Period	ITT	X
1.1.4.2	Summary of Protocol Deviations During the LTS Period	LTS Evaluable	X
1.2.1	Summary of Demographics and Baseline Characteristics in the VC Period	ITT	X
1.2.2	Summary of Demographics and Baseline Characteristics in the LTS Period	LTS Evaluable	X
1.3	Summary of Baseline Disease Characteristics	ITT	X
1.4.1	Summary of Prior Non-AD Medications	ITT	X
1.4.2.1	Summary of Prior Therapies for Atopic Dermatitis During the Past 12 Months	ITT	X
1.4.2.2	Summary of Prior Therapies for Atopic Dermatitis During the Past 12 Months by Therapy Type and Discontinuation Reason	ITT	X
1.4.2.3	Summary of Prior Therapies for Atopic Dermatitis During the Past 30 Days	ITT	X
1.4.2.4	Summary of Prior Therapies for Atopic Dermatitis During the Past 30 Days by Therapy Type and Discontinuation Reason	ITT	X
1.4.3.1	Summary of Non-AD Concomitant Medications During the VC Period	ITT	X
1.4.3.2	Summary of Non-AD Concomitant Medications During the LTS Period	LTS Evaluable	X
1.4.3.3	Summary of Concomitant Therapies for AD During the VC Period	ITT	X
1.4.3.4	Summary of Concomitant Therapies for AD During the LTS Period	LTS Evaluable	X
1.5	Summary of General Medical History	ITT	X
1.6.1	Summary of Participants With Assessments Affected by the COVID-19 Pandemic in the VC Period	ITT	X
1.6.2	Summary of Participants With Assessments Affected by the COVID-19 Pandemic in the LTS Period	LTS Evaluable	X

Table No.	Title	Population	Standard
2.2.5.1	Summary of Participants in Each Category of EASI Score in the VC Period	ITT	
Itch NRS Score			

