3.3.5.1	Shift Summary of Hematology Values – To the Worst Abnormal Value in the VC Period	Safety	X
3.3.5.2	Shift Summary of Hematology Values – To the Worst Abnormal Value in the VC Period by Age Group	Safety	X
3.3.5.3	Shift Summary of Hematology Values – To the Worst Abnormal Value in the LTS Period	LTS Evaluable	X
3.3.6.1	Shift Summary of Chemistry Values – To the Worst Abnormal Value in the VC Period	Safety	X
3.3.6.2	Shift Summary of Chemistry Values – To the Worst Abnormal Value in the VC Period by Age Group	Safety	X
3.3.6.3	Shift Summary of Chemistry Values – To the Worst Abnormal Value in the LTS Period	LTS Evaluable	X

Table No.	Title	Population	Standard
Body Weight and Height			
3.4.1.1	Summary of Body Weight and Height in the VC Period	Safety	X
3.4.1.2	Summary of Body Weight and Height in the LTS Period	LTS Evaluable	X
Vital Signs			
3.5.1.1	Summary of Systolic Blood Pressure in the VC Period	Safety	X
3.5.1.2	Summary of Systolic Blood Pressure in the LTS Period	LTS Evaluable	X
3.5.2.1	Summary of Diastolic Blood Pressure in the VC Period	Safety	X
3.5.2.2	Summary of Diastolic Blood Pressure in the LTS Period	LTS Evaluable	X
3.5.3.1	Summary of Pulse in the VC Period	Safety	X
3.5.3.2	Summary of Pulse in the LTS Period	LTS Evaluable	X
3.5.4.1	Summary of Respiratory Rate in the VC Period	Safety	X
3.5.4.2	Summary of Respiratory Rate in the LTS Period	LTS Evaluable	X
3.5.5.1	Summary of Body Temperature in the VC Period	Safety	X
3.5.5.2	Summary of Body Temperature in the LTS Period	LTS Evaluable	X

Figures

Figure No.	Title	Population
IGA		
4.1.1	Proportion of Participants Achieving IGA-TS in the VC Period	ITT
4.1.1.1	Proportion of Participants Achieving IGA-TS by Baseline IGA Score in the VC Period	ITT
4.1.1.2	Proportion of Participants Achieving IGA-TS by Baseline EASI Score in the VC Period	ITT
4.1.1.3	Proportion of Participants Achieving IGA-TS by Country in the VC Period	ITT
4.1.1.4	Proportion of Participants Achieving IGA-TS by Age Group in the VC Period	ITT
4.1.1.5	Proportion of Participants Achieving IGA-TS by Sex in the VC Period	ITT
4.1.1.6	Proportion of Participants Achieving IGA-TS by Race in the VC Period	ITT
4.1.1.7	Proportion of Participants Achieving IGA-TS by Prior TCS Therapy in the VC Period	ITT
4.1.1.8	Proportion of Participants Achieving IGA-TS by Prior TCI Therapy in the VC Period	ITT
4.1.1.9	Proportion of Participants Achieving IGA-TS by Prior Systemic Therapy in the VC Period	ITT

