2.8.2	Clinical Laboratory Values – Serum Chemistry
2.8.3	Abnormal Clinical Laboratory Values – Hematology
2.8.4	Abnormal Clinical Laboratory Values – Serum Chemistry
Body Weight and Height	
2.9.1	Body Weight and Height
Vital Signs	
2.10.1	Vital Signs
2.10.2	Abnormal Vital Sign Values
2.10.3	Alert Vital Sign Values

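### The LTS evaluable population requires an application after Week 8, so participants who enter the LTS period clear and are never re-treated drop out of its disposition and height/weight tables

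*SAP*

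**What the plan says.** SAP 5.3.5 defines the set by use of cream: "All participants who applied study drug at least once during the LTS period will constitute the LTS evaluable population". Protocol Table 12 (Section 10.2) agrees, describing a population "which includes all participants who applied study cream at least once during the LTS period". Both sections assign the LTS analyses to it; SAP 5.3.5 names efficacy and safety.

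SAP 6.2 says LTS completion, discontinuation and withdrawal "will be summarized and listed for the LTS evaluable population in the LTS period". The matching output is Table 1.1.2.2, "Summary of Participant Disposition in the LTS Period", whose population column reads LTS Evaluable. The VC paragraph of SAP 6.2 counts those "who withdrew from the study during the VC period with a primary reason for discontinuation", so it stops at Week 8.

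For safety, SAP 9.1 provides analyses "for the safety population in the VC period and for the LTS evaluable population in the LTS period". This covers SAP 9.4 and Table 3.4.1.2, "Summary of Body Weight and Height in the LTS Period", also on LTS Evaluable.

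On treatment, Protocol 4.1 lets a participant enter the LTS period with an IGA of 0 to 4, starts that period at the Week 8 visit, and puts anyone with IGA 0 into observation without treatment. Protocol Table 3 excludes the supervised Week 8 application when IGA is 0. Treatment restarts only at recurrence.

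**The concern.** Whether a clear entrant counts in the LTS period depends on something that happens after entry. A recurrence followed by one application brings the participant in. Staying clear, or withdrawing while clear, keeps the participant out. The people left out are therefore not a random subset: they include those whose response lasted longest off treatment.

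Two uses suffer most. Disposition should account for everyone who entered a period. On this set the treated row is 100% by construction, and the completion and withdrawal rows lack every entrant without an LTS application. Height and weight at Weeks 24 and 52 are scheduled for all participants, treated or not, and in children aged 2 to under 12 they are a safety measure of real interest. Children first randomized to ruxolitinib had up to 8 weeks of exposure. If never re-treated, they contribute to no visible growth summary after Week 8.

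**Working it through.** The documents state no figure on this point, so the check is mainly a trace of the rules, followed by a rough bound.

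**Trace for a participant with IGA 0 at Week 8**

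1. *Enters the LTS period?* Yes, if %BSA is within range and there is no additional safety concern (Protocol 4.1).
2. *Applies cream at the Week 8 visit?* No (Protocol Table 3).
3. *Can the last VC application count as an LTS one?* No. The Itch NRS row of Table 3 places the last VC application on the night before the Week 8 visit, and the LTS period starts at that visit.
4. *Does the three-day continuation after clearance supply an LTS application?* No. Protocol 6.1 ends it at a study visit where the IGA is 0.
5. *First LTS application?* Only on recurrence (Protocol 4.1). Protocol 4.1 and the footnote to Table 4 foresee participants in observation at IGA 0 from Week 48 or earlier to Week 52, so long clear spells are an expected pathway.
6. *If there is no recurrence, or withdrawal comes first:* not LTS evaluable.

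**Where that participant appears**

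| Output | Population in Appendix A | Included? |
|---|---|---|
| Table 1.1.2.1, VC disposition | ITT | Yes, as a VC completer only |
| Table 1.1.2.2, LTS disposition | LTS Evaluable | No |
| Table 3.4.1.2, LTS height/weight | LTS Evaluable | No |
| LTS demographics, deviations, laboratory and vital signs tables | LTS Evaluable | No |
| Baseline-to-Week 52 AE and exposure tables | Safety | Not governed by the LTS set |
| Listings 2.1.1.2 and 2.9.1 | None shown | Possibly |

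Tables 1.1.1 and 1.1.2.1 let a reader subtract the LTS evaluable N from the VC completers. The difference mixes completers who never entered the LTS period with entrants who never applied cream, and it carries no withdrawal reasons.

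**Bound on size**

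Inputs: planned arm sizes 126, 126 and 63 (Protocol Table 2); planning IGA-TS rates 51%, 47% and 14% (SAP 3.3). Baseline IGA is 2 or 3, so every IGA 0 at Week 8 is an IGA-TS response. The expected number of responders therefore caps the expected number clear:

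- 1.5%: 126 × 0.51 = 64.26
- 0.75%: 126 × 0.47 = 59.22
- Vehicle: 63 × 0.14 = 8.82
- Total: 132.3, and 132.3 / 315 = 42.0%

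Number omitted = 132.3 × *f* × *q*, where *f* is the share of responders at IGA 0 and *q* the share of those never re-treated. The documents give neither, so these values are assumptions:

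- *f* = 0.25, *q* = 0.02: 132.3 × 0.005 = 0.7 (0.2% of 315)
- *f* = 0.50, *q* = 0.10: 132.3 × 0.05 = 6.6 (2.1%)
- *f* = 0.75, *q* = 0.40: 132.3 × 0.30 = 39.7 (12.6%)

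For any common *f* and *q*, the ratio of expected omissions between the two strengths is 0.51 / 0.47 = 1.09.

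**The case against.** The strongest reply is that this is an exposure-based safety set, and height and weight sit with AEs and laboratory data in the safety objective. Adding children who used no cream after Week 8 mixes treated with untreated growth, and former-vehicle children never re-treated had no ruxolitinib at all. That argues for keeping the set for exposure and AEs, where TEAEs stop 30 days after the last dose anyway, and for showing the never-exposed children separately. It does not justify omitting entrants from disposition, or leaving the later growth of children treated in the VC period without a summary.

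A second reply is that the data still appear in listings. This stands only in part. Listing 2.9.1, "Body Weight and Height", shows no population restriction, but SAP 6.2 ties the LTS disposition listing to the LTS evaluable set as well, and a listing is not a summary.

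Third, the number may be trivial: the Protocol describes the disease as recurring, and one restart is enough to qualify. That is fair, and it limits the severity.

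Fourth, SAP text around 5.3.5 and a row of Protocol Table 12 are blacked out, so another population may exist. The visible population column for both tables still reads LTS Evaluable.

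A reader might also infer more than the documents support:

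- *That such an entrant vanishes from disposition.* The participant is in Table 1.1.2.1; only the LTS outcome is lost.
- *That this rule blocks the comparison with prior-year growth in Protocol 8.4.3.* SAP 9.4 plans visit values and changes from baseline. The prior-year comparison has no visible output for anyone.
- *That SAP 5.3.3, which puts all safety analyses on the safety population, restores these entrants.* SAP 9.1 and Appendix A are more specific and settle each visible table. That conflict is editorial.

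**Conclusion.** The gap is real and follows directly from the text: entrants clear at Week 8 and never re-treated are in the LTS period but outside its analysis set. Their LTS disposition and their Week 24 and Week 52 height and weight reach no visible summary table. Other LTS tables share the definition.

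The size is unknown. The cap of about 132 of 315 is an expected count under the planning rates, ignores dropout before Week 8, and would move with the true response rate. The span from about 1 to 40 omitted rests wholly on assumed rates. The documents do not support a claim of bias between the two strengths: under equal assumed rates the expected losses are nearly equal. Nor do they support a claim about distorted long-term disease control. No such LTS summary is visible, although the rule in SAP 5.3.5 would apply to one. The primary and key secondary endpoints and the cumulative AE and exposure tables are unaffected. This is a cheap improvement in participant accounting and growth reporting, not a threat to the trial's main conclusions.

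**What to change.** Add to the SAP an LTS-entered set: all participants who continue past Week 8 into the LTS period, by assigned or rerandomized group, whether on treatment or in observation.

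- Use it for LTS disposition (SAP 6.2, Table 1.1.2.2), with a row for entrants with no LTS application.
- Use it for LTS height and weight (SAP 9.1, 9.4, Table 3.4.1.2), showing former-vehicle entrants never exposed to ruxolitinib separately from the two vehicle-to-active groups in SAP 5.2.
- Use it for any LTS disease-severity summary that the SAP 5.3.5 rule covers.
- Keep the application-based set for exposure, AEs and application site reactions, and state which set each remaining LTS table uses.
- State LTS Day 1 and safety baseline for entrants with no LTS application. The fallback in SAP 4.1.1 covers only participants never treated, and SAP 4.1.3 has no rule for this case. One option is the Week 8 visit as LTS Day 1, with the VC baseline for participants first on active cream and the Week 8 value for those first on vehicle.
- Align the sentence in SAP 5.3.3 with 5.3.5 and 9.1.

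The cost is one population flag, two LTS denominators with a footnote, a small extra display group, and edits to SAP 4.1.1, 4.1.3, 5.2, 5.3.3, 5.3.5, 6.2, 9.1 and Appendix A. No new data are needed. The departure from Protocol Table 12 can be recorded in SAP 11.1 rather than by a Protocol amendment.

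Separately, Protocol Table 3 excludes Week 8 dispensing when IGA is 0, while Protocol 6.1 has every participant receive tubes at Week 8. These passages must be reconciled. Dispensing is not application, so the point above does not depend on the answer.
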